4.1.4 Modified Intent-To-Treat Population

The modified intent-to-treat (mITT) population will include all randomized patients who received any part of an infusion of study drug. Patients who received an incorrect therapy will be reported under the treatment arm to which they were randomized.

Patients who were not randomized but still received study treatment will be excluded from the mITT population.

All efficacy analyses will be performed using the mITT population.

4.2 ANALYSIS OF STUDY CONDUCT

Analyses of study conduct will be carried out on the safety population or all randomized patients, as appropriate.

A summary of enrollment by investigator site will be produced.

The number of patients who completed or discontinued from the study including the reason for discontinuation, will be summarized by treatment group. A listing of early discontinuations will be produced.

Major protocol deviations will be listed. Any study conduct that is impacted by COVID-19 or Ukraine-Russia conflict will be summarized in the final CSR.

Patient duration in the entire study will be summarized. Duration will be calculated as:

$$\text{date of last visit} - \text{date of the first dose} + 1$$

Previous and concomitant medications will be summarized descriptively by mapped term and treatment group. A summary of rescue medications will also be produced.

A summary of the number of patients who experience treatment failure along with the reason(s) for treatment failure will be produced. The number of patients receiving rescue will also be listed and summarised.

A summary of exposure to study treatment will be produced using the dose recorded on the electronic case report form (eCRF). The number of obinutuzumab/placebo infusions and dose received at each infusion and overall will be summarised by treatment group. The total cumulative dose of obinutuzumab/placebo over the 52-week treatment period will be summarised. Note that these summaries highlight adherence to the blinded study treatment and not exposure to the active treatments (which will be described separately). Proportion of patients received rescue medication will be summarized by treatment group.

4.3 ANALYSIS OF TREATMENT GROUP COMPARABILITY

Demographic and baseline disease characteristics will be summarized as described in the following sections.

4.3.1 Demographics

Demographics will be summarized, including:

- Sex
- Age (years)
- Height (cm)
- Weight (kg)
- Body mass index (kg/m²)
- Race
- Ethnicity
- Region
- Smoking status
- Female reproductive status

4.3.2 Disease Characteristics

Baseline values will be summarized, including:

- Duration of LN (months)
- Duration of systemic lupus erythematosus (SLE) (months)
- Estimated glomerular filtration rate (eGFR) calculated using the CKD-epi formula
- Urine red blood cells (RBCs), white blood cells (WBCs) and RBC casts

Obinutuzumab—F. Hoffmann-La Roche Ltd

Statistical Analysis Plan

WA29748

- Serum creatinine
- Urinary Protein to Creatinine Ratio
 - 24-hour urine sample and from random sample
- LN biopsy class:
 - Proportion of patients with Class III
 - Proportion of patients with Class IV
 - Proportion of patients with concomitant Class V
 - NIH activity and chronicity scores

Medical history data, including surgery and procedures, MMF/mycophenolic acid (MPA) (including dose) and cyclophosphamide use, and baseline conditions will be summarized descriptively by treatment group using the safety population. A glossary showing the mapping of investigator verbatim terms to diseases will be produced for the medical history data.

4.4 DATA-CUT FOR ANALYSES

All data in the final database will be reported, unless otherwise specified in the relevant sections of the SAP.

4.5 VISIT WINDOWS

In general, data for assessments that are collected by scheduled visits will be mapped to visits that appear in the schedule of assessments ([Appendix 2](#)) per the protocol using the actual study day of assessment. Data mapped to scheduled visits will include all data collected up to the final database lock, and may include withdrawal visits and unscheduled visits. Data will never be mapped to visits for which the assessment was not scheduled in the protocol (i.e., results for an assessment conducted at an unscheduled visit will be mapped to the appropriate visit at which the assessment was scheduled). Visit windows will be continuous from the midpoint between two consecutive study visits, and will be dependent on the schedule of assessments for each variable independently. An example of the urinalysis visit window is given in [Table 1](#). Visit windows for each variable will be constructed in the same manner.

Table 1 Time Windows of Study Days to Assign Study Visit for Urinalysis

Study Visit	Scheduled Study Day	Actual Study Day Time Window
Baseline	1	≤ 1
Week 4	28	$2 \leq \text{day} < 57$
Week 12	84	$57 \leq \text{day} < 127$
Week 24	168	$127 \leq \text{day} < 211$
Week 36	252	$211 \leq \text{day} < 309$

Week 52	364	309≤day<425
Week 76	532	425≤day<631
Week 104	728	631≤day<789
BCFU	>789	

BCFU=B-cell follow up

Derived variables that are collected on an ongoing basis will be presented using appropriate time intervals. For primary analysis at Week 52, the upper limit of the visit window will be Day 364 + 60 days. For Week 104, the upper limit of the visit window will be 728 + 60 days. For BFU, the visit is scheduled every 6 months.

Data displays that are presented by visit will only include visits at which the assessment was scheduled to be collected. The methods for handling multiple values within a visit window are described in Section 4.9.3.

4.6 EFFICACY ANALYSIS

The primary and secondary efficacy analyses will include all randomized patients who received any study medication, with patients grouped according to the treatment assigned at randomization.

The primary and secondary endpoints will be tested at an overall 20% significance level using two-sided hypothesis tests.

The primary and secondary efficacy endpoints are listed below:

1. Proportion of patients that achieve a CRR at Week 52
2. Proportion of patients who achieve an overall response at Week 52 (CRR+PRR)
3. Proportion of patients that achieve a modified CRR (mCRR1) at Week 52 employing the primary-efficacy measure definition and removing the urinary sediment analysis criteria
4. Proportion of patients that achieve a second modified CRR (mCRR2) at Week 52
5. Change in anti-dsDNA titers
6. Change in C3 levels
7. Change in C4 levels
8. Time to overall response (CRR+PRR) over the course of 52 weeks
9. Proportion of patients that achieve a PRR at Week 52
10. Time to CRR, over the course of 52 weeks
11. Proportion of patients that achieve a third modified CRR (mCRR3) at Week 52
12. Proportion of patients who achieve a CRR at Week 24

Obinutuzumab—F. Hoffmann-La Roche Ltd

Statistical Analysis Plan

WA29748

If at any step in the testing procedure, the p-value associated with a test is not <0.20 , the remaining endpoints below the sequence will not be considered statistically significant. The final CSR will include all the primary and secondary endpoints in order of testing for completeness.

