### **OBJECTIVES**

#### **EFFICACY OBJECTIVES**

The primary efficacy objective for this study is as follows:

- To evaluate the efficacy of obinutuzumab compared with placebo in patients with International Society of Nephrology (ISN)/Renal Pathology Society (RPS) Class III or IV lupus nephritis (LN) as measured by complete renal response (CRR) at 52 weeks

The secondary efficacy objectives for this study are as follows:

- To assess overall renal response (defined as CRR plus partial renal response [PRR])
- To evaluate the ability of obinutuzumab to improve time-to-response (CRR plus PRR) over the course of 52 weeks

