response (weighted toward complete renal response [CRR]); no major new safety signals were identified. The LUNAR study determined that the combination of rituximab + MMF was more effective at reducing anti-dsDNA autoantibody levels and increasing complement levels than MMF alone. In addition, there was a 15.3% increase of partial renal response (PRR) with rituximab, and fewer patients in the rituximab arm required rescue with cyclophosphamide (n=1) versus the MMF-alone arm (n=8). A pre-specified sub-analysis of African American patients (n=40) demonstrated that 70% of these patients responded (PRR+CRR) in the rituximab arm versus 45% in the MMF-alone arm (p=0.2) (Rao et al. 2012). This analysis clarified that non-responders had higher mean serum creatinine levels, a higher degree of proteinuria, and higher mean blood pressure than did responders.

The partial response observed in the LUNAR study, in addition to the multiple publications that suggest partial response in patients with more refractory disease (Lu et al. 2009; Jónsdóttir et al. 2010; Roccatello et al. 2011; Turner-Stokes et al. 2011; Díaz-Lagares et al. 2012; Gregersen and Jayne 2012; Furtado and Isenberg 2013), particularly with the combination of rituximab and cyclophosphamide (Ng et al. 2007), has suggested that rituximab has a place in the treatment of these patients and led to its incorporation into the ACR LN Treatment Guidelines in 2013 (Hahn et al. 2012). This partial response difference along with the improvement in anti-dsDNA antibody and complement levels suggests that the drug has activity, but not at the level of CRR. These findings, in addition to lupus-related factors described below that might impair rituximab's ability to deplete B cells in SLE, are consistent with the hypothesis that incomplete local B-cell depletion contributed to a partial response and that a more efficient B-cell depleting agent (obinutuzumab) might be associated with greater efficacy.

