### **6.4.1 Primary Efficacy Endpoint**

The primary assessment of efficacy of obinutuzumab, to induce a clinically significant improvement in renal function in patients with ISN/RPS 2003 class III or IV LN, will be assessed by attainment of CRR.

CRR is defined as achievement of all of the following:

- Normalization of serum creatinine as evidenced by the following:
  - Serum creatinine  $\leq$  the ULN range of central laboratory values if the baseline (Day 1) serum creatinine is above the ULN
  - Serum creatinine  $\leq$  15% above baseline and  $\leq$  the ULN range of central laboratory values if baseline (Day 1) serum creatinine is  $\leq$  the ULN range of central laboratory values
- Inactive urinary sediment (as evidenced by  $< 10$  RBCs/HPF and the absence of red cell casts)
- Urinary protein to creatinine ratio  $< 0.5$

Any patient who switches to rescue medication prior to Week 52 will be considered a non-responder. Additional criteria for analyses of patients who are considered non-responders will be specified in the SAP.

The proportions of patients achieving CRR across treatment groups will be compared using a CMH test with race (Afro-Caribbean/African American versus others) and region (United States versus non-United States) as stratification factors. If the test result is in favor of the obinutuzumab group at  $\alpha < 0.1$ -level (one-sided), it will be concluded that there is a shift toward better renal response associated with the obinutuzumab group.

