4.6.2 Secondary Efficacy Endpoints

4.6.2.1 Overall Renal Response

The proportion of patients who achieve an overall response at Week 52 (CRR+PRR) will be analyzed using a CMH test, with race and region as strata.

The proportion of patients achieving PRR at Week 52 as defined by achievement of all of the following:

- Serum creatinine $\leq 15\%$ above baseline value
- No urinary red cell casts and either RBCs/HPF $\leq 50\%$ above baseline or < 10 RBCs/HPF
- 50% improvement in the urine protein to creatinine ratio, with one of the following conditions met:
 - If the baseline urine protein to creatinine ratio is ≤ 3.0 , then a urine protein to creatinine ratio of < 1.0
 - If the baseline protein to creatinine ratio is > 3.0 , then a urine protein to creatinine ratio of < 3.0

Missing Data

Missing data for each component of the endpoint will be imputed using the relevant approach discussed in Section [4.6.1](#).

Time to First Overall Response

Time to first overall response (CRR+PRR) over the course of 52 weeks will be presented using Kaplan-Meier methodology and compared between treatment groups using a stratified log-rank test with race and region as strata. Time to CRR during this period will be analyzed similarly.

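### Must the SAP say that partial response excludes complete response, and require each step of the sequence to favour obinutuzumab?

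*SAP*

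**What the plan says.** SAP 4.6 orders twelve endpoints. Step 1 is CRR at Week 52, step 2 is "Proportion of patients who achieve an overall response at Week 52 (CRR+PRR"), and step 9 is "Proportion of patients that achieve a PRR at Week 52". Steps 10 to 12 are time to CRR, mCRR3 and CRR at Week 24. On the tests it says: "The primary and secondary endpoints will be tested at an overall 20% significance level using two-sided hypothesis tests". The stopping rule begins "If at any step in the testing procedure, the p-value associated with a test is not" and sets the limit at 0.20; endpoints after a failed step are not called significant. The rule does not mention direction. The section also commits the final report to showing every primary and secondary endpoint.

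SAP 4.6.2.1 introduces the partial-response criteria with "The proportion of patients achieving PRR at Week 52 as defined by achievement of all of the following" and lists creatinine, sediment and UPCR conditions. No condition removes patients who meet CRR. The section names a CMH test for overall response and none for PRR alone. Protocol 3.4.1 and 6.4.2 are silent on the same points.

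The one directional condition is in Protocol 6.4.1, for the primary endpoint: "If the test result is in favor of the obinutuzumab group at" the one-sided 0.1 level. Appendix 1 of the SAP repeats it.

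**The concern.** The protocol's efficacy objective, "To assess overall renal response (defined as CRR plus partial renal response [PRR"]), reads like a sum of two separate categories. Protocol 1.3 describes earlier rituximab results in similar terms: the partial-response difference "suggests that the drug has activity, but not at the level of CRR". If the categories are separate, PRR does not rise steadily with benefit, because a patient who moves from partial to complete response leaves it. A two-sided gate then passes on a large enough PRR deficit, and time to CRR, mCRR3 and Week 24 CRR could be labelled significant after an apparently adverse step 9. If the categories are nested, step 9 adds almost nothing to step 2. Two programmers could choose differently, and the label on the last three endpoints could depend on the choice.

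**Working it through.** **1. The plan's own figure.** Inputs from SAP 2.3: 60 per arm, CRR 30% v 50%, two-sided alpha 0.20 (critical value 1.2816). Pooled normal approximation:

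(0.20 − 1.2816 × √(2 × 0.4 × 0.6 / 60)) / √((0.3 × 0.7 + 0.5 × 0.5) / 60) = (0.20 − 0.1146) / 0.0876 = 0.975, so power is 83.5%.

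This reproduces the stated 83%.

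**2. Does CRR imply PRR on the written criteria?**

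- *Creatinine.* With baseline at or below the ULN, CRR already requires no more than 15% above baseline. With baseline above the ULN, CRR requires a value at or below the ULN, which is below baseline. Both satisfy PRR.
- *Sediment.* CRR's fewer than 10 RBCs/HPF and no red cell casts satisfy PRR.
- *UPCR.* CRR requires below 0.5. With baseline at least 1.0, half of baseline is at least 0.5, so the 50% improvement holds, and 0.5 is under both the 1.0 and 3.0 limits.

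On a grid of 5,550 pairs of baseline and Week 52 UPCR (Week 52 below 0.5), no pair with baseline at least 1.0 failed the PRR criterion; 130 pairs with baseline below 1.0 did. Entry requires UPCR above 1.0 (Protocol 4.1.1), and a missing Day 1 value is replaced first by the screening 24-hour value (SAP 4.6.1.4). The exception therefore needs a measured Day 1 value below 1.0. Read literally, step 9 is close to step 2.

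**3. The partial-only reading.** Here PRR-only = overall response − CRR. With the planned 20-point CRR gain, any overall gain below 20 points gives an expected PRR deficit. A modest one is enough for p<0.20. By the Mantel-Haenszel statistic, placebo 15/60 v obinutuzumab 9/60 (24 responders in all) gives

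z = (9 − 12) / √(60² × 24 × 96 / (120² × 119)) = −3 / 2.200 = −1.364, two-sided p = 0.173.

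**4. How often.** Simulated trials use 60 per arm, CRR 30% v 50%, and the unstratified test at two-sided 0.20. Steps 1 and 2 count as passed only if they favour obinutuzumab. Steps 3 to 8 are not modelled, so the last three columns are upper bounds for opening steps 10 to 12. The plan gives no PRR rates; all of these are assumptions.

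| PRR-only, placebo v obinutuzumab | Step 9 fails | Step 9 passes on a deficit | Steps 1–2 pass, step 9 passes on a deficit | Steps 1–2 pass, step 9 passes either way | Same, direction required |
|---|---|---|---|---|---|
| 20% v 20% | 79.4% | 10.3% | 6.4% | 12.9% | 6.5% |
| 20% v 15% | 68.6% | 29.1% | 13.6% | 15.0% | 1.3% |
| 20% v 10% | 38.6% | 61.2% | 19.7% | 19.8% | 0.1% |
| 24.7% v 16.9% | 57.3% | 41.7% | 16.3% | 16.8% | 0.5% |
| 16% v 31.3% | 23.4% | 0.1% | 0.1% | 61.7% | 61.7% |

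The fourth row is the ocrelizumab trial's overall response (54.7% v 66.9%, Protocol 1.3) minus this trial's planned CRR. The fifth starts from the 46% control response in the earlier rituximab trial (100% − 54% with no response) minus 30%, and adds that trial's 15.3-point PRR increase. Both mix studies, and the fifth implies 81.3% overall response on obinutuzumab.

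**5. Would redefining PRR now be harmless?** Not necessarily. Take 60 per arm, obinutuzumab v placebo: CRR 25 v 18 (p = 0.18) and overall response 41 v 28 (p = 0.017). Suppose seven obinutuzumab complete responders had Day 1 UPCR below 1.0 that was not halved. Literal PRR is 41 − 7 = 34 v 28, p = 0.28, and the gate closes. PRR-only is 41 − 25 = 16 v 28 − 18 = 10, p = 0.19, and the gate opens. The case is unlikely, but it shows that a late redefinition can add a significance label.

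**The case for a change.** The strongest case for a change is that neither reading serves step 9 well: one makes it redundant, and the other lets an adverse result open efficacy claims. The protocol left the ordering and the detail of the secondary analyses to the SAP (Protocol 3.4.1 and 6.4.2), and two sentences would settle both matters.

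The textual gaps and the arithmetic stand. The harm largely does not.

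- A reader of the final report can see what happened. SAP 4.9.1 presents all displays by treatment group, with number and percentage for categorical data, and SAP 4.6 reports every endpoint whatever the gate does. The two arm percentages show the direction. If PRR and CRR counts add up to overall response, the categories are separate; if PRR nearly equals overall response, they are nested.
- Partial-only is not clearly the intended reading. The sum-like label leans that way, but 4.6.2.1 gives a list of criteria that is complete on its face, and the remarks in Protocol 1.3 concern other trials.
- Writing in the partial-only definition would impose the very derivation that creates the deficit problem. Adding a directional gate would then close steps 10 to 12 in almost every trial where the drug works by turning partial into complete responders (19.8% to 0.1% in the 20% v 10% row).
- The Week 52 and Week 104 reports already exist (SAP 1), so a new definition now could depart from the one already used.

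The unnamed test for PRR alone is a similar omission. The stratified CMH test used for the other response proportions is the natural choice.

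**Conclusion.** No change to the plan is needed. Following it as written gives no wrong result. A fixed sequence of two-sided tests at 0.20 controls familywise error for the two-sided hypotheses, and Protocol 6.4.1 already ties the primary conclusion to a result favouring obinutuzumab. What remains is the significance label on time to CRR, mCRR3 and Week 24 CRR in a 120-patient proof-of-concept study.

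Under the partial-only reading, the share of trials that pass steps 1 and 2 and then pass step 9 on a deficit runs from 0.1% to 19.7%. It is negligible if PRR rises by the amount quoted for rituximab. It is appreciable only if the drug mainly converts partial responders, and even then it is an upper bound because steps 3 to 8 must also pass. Under the literal reading, step 9 is mostly a repeat of step 2.

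These sizes rest on assumed PRR rates, the planned CRR rates, no stratification, and a Mantel-Haenszel test for PRR. The absent clause is a detail that analysts fill by keeping the derivation already used in the reported analyses. Requiring direction at every step is a matter of preference with a real cost.

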4.6.1 Primary Efficacy Endpoint

The primary efficacy endpoint is the proportion of patients achieving CRR at Week 52.

The following two-sided hypothesis will be tested at the 20% significance level (double-sided):

$$H_0: \rho_{MMF+OBZ} - \rho_{MMF+PBO} = 0$$

$$H_1: \rho_{MMF+OBZ} - \rho_{MMF+PBO} \neq 0$$

where ρ denotes the proportion of patients achieving complete renal response; PBO=Placebo; and OBZ=Obinutuzumab. The clinical meaningful difference is 15%.

The primary method for comparing the proportion of patients achieving sustained complete remission will be the CMH test. The analysis will be stratified by the stratification factors applied at randomization. The proportion of patients achieving sustained complete remission in each treatment group will be presented along with the adjusted difference, 95% confidence interval for the difference, and p-value.

4.6.1.1 Complete Renal Response at Week 52

A patient will be considered a responder for complete renal response if all of the following conditions are met at the Week 52 visit:

- Normalization of serum creatinine as evidenced by the following:
 - Serum creatinine \leq the upper limit of normal (ULN) range of central laboratory values if baseline (Day 1) serum creatinine is above the ULN
 - Serum creatinine \leq 15% above baseline and \leq the ULN range of central laboratory values if baseline (Day 1) serum creatinine is \leq the ULN range of central laboratory values
- Inactive urinary sediment as evidenced by:
 - <10 RBCs/high-power field (HPF) and
 - the absence of red cell casts
- Urinary protein to creatinine ratio <0.5

Any patient who switches to rescue medication will be considered a non-responder.

Patients who discontinue early from the study or meet the criteria for treatment failure will be evaluated using data up to the point of withdrawal or treatment failure only, whichever occurs first. They will be deemed non-responders.

Complete renal response is a composite endpoint derived using several sources of information. Methods for data handling and dealing with missing data for the components of the primary endpoint are provided below. Any missing or ambiguous data will be queried and all efforts will be made to resolve data issues prior to database lock.

If any of the conditions for complete renal response are still missing after the below imputation rules are applied, then the patient will be set to non-responder.

4.6.1.2 Serum Creatinine

Only creatinine data obtained from the central laboratory will be used for efficacy analysis.

Missing Data: If Day 1 serum creatinine data is missing, then the screening value will be used. Missing post-baseline serum creatinine will be imputed using the value from the previous visit. If the previous visit is still missing, no imputation will be made, unless otherwise specified.

4.6.1.3 Inactive Urinary Sediment

Urine sediment data from the local laboratory will be prioritized in the efficacy analysis given the time-sensitive nature of this analysis and the delay between local specimen collection and central laboratory analysis. The central laboratory data will be used when local laboratory data are missing using the strategy highlighted below.

Missing Data

Missing urine sediment data at Day 1 will be imputed in the following order:

- Urine sediment data at Day 1 (central lab)
- Urine sediment data from screening (local lab)
- Urine sediment data from screening (central lab)

Missing post-baseline RBC counts will be imputed in the following order:

- RBC counts at the same visit (central lab)
- RBC counts from the previous visit (local lab)
- RBC counts from the previous visit (central lab)

If the value is still missing, then no imputation will be made.

Missing post-baseline RBC casts will be imputed in the following order:

- RBC casts at the same visit (central lab)
- RBC casts from the previous visit (local lab)
- RBC casts from the previous visit (central lab)

If the central laboratory value from previous visit is still missing, then “casts absent” will be imputed.

